7.4.2. Field training

On the second training day, simulated buyers will practice fieldwork at nearby e-cigarette stores with coordinators accompanying them. The goal of the field training is to further enhance the simulated buyers' understanding of the process, proficiency in memorizing details, and ability to complete the questionnaire

The practice in the field will be conducted by a single simulated buyer, and the process will be exactly the same as the formal trial. Sellers in the e-cigarette stores will not be aware that they are being studied, and the physical environment will be recorded by the coordinators beforehand. During the field training, the coordinator will wait outside e-cigarette stores and discuss the difficulties and problems encountered after the survey is completed, to help them effectively develop skills for data collection. Each simulated buyer will try several stores until they are familiar with the entire process and get more than 90% of the objective items in the questionnaire correct. Otherwise, they will be taken to the next e-cigarette store to continue their field practice. The entire training will last 3-5 days.

7.5. Randomization

Each simulated buyer will be assigned with a random number and the clusters of e-cigarette stores will be randomly allocated to the intervention group or the control group before the visits. Details on randomization can be found in **Section 7.1.3.** Randomization and assignment of all simulated buyers and e-cigarette stores will be completed before the start of the formal survey.

7.6. Study visits and treatment procedures

The formal study will begin in July 2023. The simulated buyers and coordinators will be

divided into three teams, each including eight simulated buyers[†] (18-19 years old) and two coordinators (graduate students). Each team will travel from Beijing to all the metropolitan areas across mainland China (Appendix 8).

Simulated buyers will travel to new metropolitan areas by train or air and change into the prepared attire at the hotel (the type of attire worn on that day will be pre-determined by a random number). The team coordinator will then assign a list of pre-specified e-cigarette stores to each simulated buyer. Using the assistance of the AutoNavi Map, simulated buyers will travel by public transportation according to the geographic information on the list to the e-cigarette stores to conduct the survey. Each simulated buyer will visit 4-5 e-cigarette stores per day if possible.

The simulated buyers will take on the role of an adolescent who attempt to buy e-cigarette products, go into a store, talk to the seller, and try to make the purchase. They will record all the information using Questionnaire Star (an App) on their smart phone after the visit is completed. Upon the arrival, the simulated buyers will first observe the external environment of the store out of sight of the seller and fill in the related information. They will then enter the store, purchase e-cigarette products, and record seller responses and the internal environment of the store. After memorizing the information, they will leave the store, complete, and submit the data collection form online. The same simulated buyer will conduct a similar trial in one of the nearest cigarette stores, which serves as a match to the e-cigarette store that he or she just visited. After completing the visit, they will then travel to the next e-cigarette store. Survey details and measurements can be seen in **Section 5** and **Section 6**.

The coordinators will provide them with necessary help and answers to their queries during the fieldwork. If any of the included stores happen to be closed or unavailable, the coordinators will direct them to the nearest alternative e-cigarette store from the replacement list. If the number of inaccessible stores is too high, the coordinators will search for available e-cigarette stores nearby the simulated buyers and confirm their operating status at that time by phone, and then assign simulated buyers to go to survey them when possible.

[†] One team will include 4 male and 5 female adolescent buyers due to the inclusion of an extra female data collector.

Each team will need at least one day to complete the survey in one metropolitan area, and the survey is expected to last between 3 and 5 weeks, considering the long distances between study sites (metropolitan areas), uncertain weather conditions, delayed transportation, and illness of personnel. The survey is scheduled to be fully completed by September 2023 for the data collection in all 36 metropolitan areas across mainland China.

8. Statistical Analyses

8.1. General statistical methods

Summary statistics will be presented for both the treatment and control groups. Continuous variables will be summarized by the number of observations, mean, standard deviation, median, minimum, and maximum. Categorical variables will be summarized using frequency counts and percentages. Descriptive analyses of the distributions of the e-cigarette seller behavior outcomes between two types of attire (treatment and control groups), including successful purchases, inquiring about buyer age, requesting ID cards for age verification, and dissuading buyers from use, as well as store environment features, and sellers' demographic characteristics, will be conducted with t-tests and chi-square tests detecting statistically significant differences.

The significance level for comparisons between the two groups is set at $\alpha=0.05$ (two-sided). Differences between the study groups will be considered statistically significant if the p-value is less than 0.05. All analyses will be performed using Stata MP 17.

8.2. Analysis of primary outcome

For the primary outcome, successful purchase rates will be analyzed using Chi-square tests to determine if the differences between the treatment group and the control group are statistically significant. Multivariate logistic regression models will be further employed to analyze the treatment effect, adjusting for covariates.

A national map depicting the geographic variations in the outcomes of successful purchase rates will be created using the R package DrawChinaMap.

8.3. Analysis of secondary outcomes

Secondary outcomes, including inquiring about the buyer's age, requesting ID cards for age verification, and dissuading buyers from use, will be analyzed in a similar manner to the primary outcome. Chi-square tests will be used to detect the statistical significance of differences between the two study groups, and logistic regression models, adjusted for covariates and appropriate for the distribution of the outcomes, will be employed. Additionally, similar national maps describing geographic variations will be generated.

8.4. Analysis of other outcomes

Other outcomes, including illegal flavored products, online contact, and delivery service offered, will be analyzed in a similar way as the primary outcome. Chi-square tests will be used to detect statistical significance in differences between the two groups, and logistic regression models appropriate for the distribution of the binary outcomes with covariate adjustments will be employed. Similar national maps describing geographic variations will be generated as well. For marketing claims and strategies, we will further employ thematic framework analysis to qualitatively analyze and describe the marketing methods and tactics of e-cigarette stores.

8.5. Subgroup analysis

For matched e-cigarette and cigarette stores, we will employ McNemar's tests to assess the distinctions in the outcomes between e-cigarette stores and cigarette stores. Rates of successful e-cigarette purchases stratified by age checking behaviors and buyer attire will also be reported. Planned subgroup analyses are intended to explore potential effect modifications of gender, age, metropolitan area and store types.

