7.1.3. Randomization

Prior to the randomization of subjects, all the eligibility criteria must be met.

- **Generating clusters to which the stores belong:** Considering traveling time and the efficiency of data collection, this trial will use a cluster randomization approach, rather than simple randomization. Investigators will firstly map all the 40 selected stores within each metropolitan area, then divide them into clusters that contains the same number (usually 4 stores) considering their locations and public transportation. Then each cluster will be digitally labeled, from area 1 to area 8. The labeling of the clusters follows the principle of from top to bottom, from left to right on the map.
- **Assigning clusters to treatment:** Each cluster will be randomly assigned to one simulated buyer, and the attire (school uniforms or casual attire) he/she wears on a specific day will also be random. In this way, the e-cigarette stores will finally be allocated at a 1:1 ratio to either the intervention or control group.
 - (1) Specifically, the simulated buyers (data collectors) to be recruited are 18 to 19 years old, with a 1:1 ratio of males to females. To reduce bias associated with personal characteristics of simulated buyers, they will be randomly assigned a new digital number for each metropolitan area, which is used for matching the clusters.
 - (2) The type of attire wore by each adolescent on a specific day will be pre-determined using the Excel's random number generator within each sex, and each adolescent will have an equal probability to wear school uniforms and casual attire during the entire study.

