7.3. Data collector recruitment

We plan to recruit 25 college students in Beijing through social media in June-July 2023, including 12 males and 13 females, where the one additional female data collector will be recruited considering that females may need to take some days off during the fieldwork due to health-related reasons. This way, a gender-balanced sample will be more likely to be achieved.

Requirements including:

- Aged 18 or 19 years old (according to the WHO standard, adolescents are defined to less than 20 years old)
- Having never used any tobacco products including e-cigarettes and cigarettes

- No apparent dyed hair
- No tattoos being seen

A poster will be designed and posted in WeChat Moments and online forums to recruit the simulated buyers in Beijing. It also will be shared among faculty, staff, and students at several universities in Beijing. The poster will contain the following information, including study title, location, time of the investigation, requirements, compensation, and contact information. Considering the need to keep the study confidential from Chinese e-cigarette retailers, the investigators will avoid mentioning too many details in the recruitment poster and only inform adolescents of more specific information in the subsequent interview sessions.

The coordinator will create a WeChat group of the adolescents who sign up. In July 2023, an online interview will be performed to communicate with those who are willing to take part in, providing them with more details about the trial, and check whether they are eligible for the investigation.

Each simulated buyer will receive CNY 350 (approximately USD 50) per day as payment and all accommodation and transportation costs will be covered by the study.

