### **2.2.2. Covariates**

The assessment tool should be designed primarily based on the Vape Shops Standardized Tobacco Assessment for Retail Setting (V-STARS) and the Tobacco Advertising, Promotion and Sponsorship (TAPS) bans compliance guide, as well as published articles. It will be further adapted by investigators who are familiar with Chinese e-cigarette retailers and laws and have observed store characteristics, to the Chinese context to collect information mainly on store internal/external environmental features (e.g., location, advertising, warning signs, and licensing), product availability, and seller behaviors. Detailed information on covariates is listed as below:

- Buyer characteristics: Sex, Age
- Seller characteristics: Sex, Age perceived by the simulated buyers (18-29, 30-40, >40 years old)
- Store characteristics: Store location (In mall, on street), region, age-of-sale warning sign presented, license to sell e-cigarettes presented, health warning presented, and advertising.

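### If the planned gender and age subgroups mean the buyer's, the contrast rests on 25 buyers, and store-level interaction tests would declare effect modification too often

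*Protocol*

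**What the plan says.** The subgroup sentence is identical in Protocol 8.5 and SAP 2.3.5: "Planned subgroup analyses are intended to explore potential effect modifications of gender, age, metropolitan area and store types". No interaction test is specified. SAP 2.2.2 lists "Buyer characteristics: Sex, Age" and also "Seller characteristics: Sex, Age perceived by the simulated buyers", so gender and age could belong to either party.

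On the buyers, Protocol 7.3 says "We plan to recruit 25 college students in Beijing through social media in June-July 2023, including 12 males and 13 females", each "Aged 18 or 19 years old". On allocation, Protocol 7.1.3 says "Each cluster will be randomly assigned to one simulated buyer, and the attire (school uniforms or casual attire) he/she wears on a specific day" is also random, and that "each adolescent will have an equal probability to wear school uniforms and casual attire during the entire study". Protocol 7.6 adds "Each simulated buyer will visit 4-5 e-cigarette stores per day if possible".

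For the attire effect, Protocol 8.2 and SAP 2.3.2 name chi-square tests and covariate-adjusted logistic regression. No section mentions a buyer effect, a cluster term or a cluster-robust standard error.

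**The concern.** A buyer has one sex and, for practical purposes, one age, and makes about 43 e-cigarette store visits in both outfits. Asking whether the attire effect differs between male and female buyers therefore compares the attire effects of 12 people with those of 13 others. A store-level model with an attire-by-sex term counts about 1,080 independent observations instead.

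Two sources of variation are then left out. One is correlation among the stores a buyer visits on one day, when attire and buyer sex are both constant. The other is person-to-person variation in how much the uniform changes the seller's response. Protocol 5.3 makes the second plausible: it says a uniform marks the wearer as a minor above all when the wearer looks young.

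At stake is a reported finding, for example that uniforms protect more when the buyer is female, that reflects which students happened to be hired.

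**Working it through.** **No plan figure to reproduce.** The documents give no number for any subgroup test. The overall size (about 1,080, said to be about three times the minimum, so a minimum near 360) cannot be reproduced, because Protocol 8.6 leaves the purchase rates to the pilot.

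**Inputs from the documents.** 25 buyers, 12 male and 13 female; about 1,080 stores; 4 stores per buyer-day; ICC 0.5; two-sided 0.05. Per buyer: 1,080/25 = 43.2 stores, and 43.2/4 = 10.8, taken as 11 buyer-days. The simulated trial has 25 × 11 × 4 = 1,100 stores.

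**Assumed.** Purchase rates casual/uniform of 70%/40% or 69%/45%; buyer intercept SD 0.5 to 1.0 logit; buyer-day variation as stated below; slope SD τ (the between-buyer SD of the attire log-odds ratio) of 0 to 1.0. The true sex-by-attire interaction is zero.

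**Step 1: buyer-day clustering at the plan's own ICC.** Design effect = 1 + (4 − 1) × 0.5 = 2.5. Attire and buyer sex are constant within a buyer-day, so all of it applies to this interaction. A nominal 5% store-level test then rejects with probability 2[1 − Φ(1.96/√2.5)] = 2[1 − Φ(1.24)] ≈ 21%, before any buyer variation in the attire effect. This reads 0.5 as a correlation of the observed outcomes; read as a latent correlation, it gives the 18% in step 3.

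**Step 2: what τ adds.** The interaction is a difference between two differences in log-odds. Its store-level variance is Σ 1/[n p(1 − p)] over four cells. With 264 stores per cell for males, 286 for females, and rates 70%/40%:

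1/(264 × 0.21) + 1/(264 × 0.24) + 1/(286 × 0.21) + 1/(286 × 0.24) = 0.0180 + 0.0158 + 0.0167 + 0.0146 = 0.065.

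Buyer slopes add τ²(1/12 + 1/13) = 0.160τ². More stores per buyer do not reduce this term.

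- τ = 0.5: variance ratio (0.065 + 0.040)/0.065 = 1.62; rejection 2[1 − Φ(1.96/1.27)] ≈ 12%.
- τ = 1.0: variance ratio (0.065 + 0.160)/0.065 = 3.46; rejection 2[1 − Φ(1.96/1.86)] ≈ 29%.

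These are rough values that leave out buyer-day correlation.

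**Step 3: simulation.** Rates 70%/40%, 2,500 runs per setting. Ranges are over four combinations of buyer intercept SD (0.5, 1.0) and buyer-day SD (0 to 1.0). The Monte Carlo standard error near 5% is √(0.05 × 0.95/2,500) = 0.4 points. The buyer-level test is a t-test on each buyer's attire log-odds ratio.

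| τ | Stores independent | Buyer-day clustered | Buyer-level t-test |
|---|---|---|---|
| 0 | 9.0-13.1% | 5.0-6.6% | 3.9-4.9% |
| 0.3 | 10.6-14.6% | 6.2-7.4% | 4.4-6.0% |
| 0.5 | 13.0-17.5% | 8.0-9.4% | 4.0-4.8% |
| 0.75 | 20.8-22.2% | 11.3-14.9% | 4.6-5.7% |
| 1.0 | 26.3-27.4% | 15.3-19.4% | 4.8-5.6% |

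A second set used rates 69%/45%, buyer intercept SD 0.5 and latent buyer-day ICC from 0 to 0.5. The store-level test rejected about 7-18% at τ = 0 and about 25% at τ = 1.0. Buyer-day clustering gave 5-6% at τ = 0, 7-11% at τ = 0.5 and 10-19% at τ = 1.0. The lowest values came at ICC 0.5 (6.8% at τ = 0.5, 9.9% at τ = 1.0), because day-to-day noise then swamps the slope variation. A buyer-level t-test on rate differences stayed at about 5%.

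**Step 4: age.** The documents give no split between 18 and 19. With an assumed 6/19 split, buyer-day clustering gives 5.6%, 9.5% and 20.8% at τ = 0, 0.5 and 1.0. Standard errors clustered on buyer give 8.2-8.7%, and the buyer-level t-test 4.6-5.5%.

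**The case against.** - **Whose gender and age.** The documents do not say. Seller sex and perceived age are recorded at every visit (Protocol Appendix 4, items 19 and 20) and vary from store to store, so under that reading the 25-buyer argument fails. The buyer reading is plausible, because buyer sex is randomly assigned (5.1), attire is drawn within sex (7.1.3) and a gender-balanced set of buyers is sought (7.3). It is not certain. This stands, and the point is conditional on it.
- **Buyer-day clustering.** A reader might infer that even a buyer-day-clustered analysis would declare modification too often. The documents do not support that. Each buyer wears both outfits, so buyer main effects largely cancel, and the clustered test is close to nominal unless attire effects differ between buyers. No figure for that variation is given, and the plan does not mention such an analysis.
- **Size of τ.** Standard clothing, a conversation guide and field training limit buyer variation. At rates 69%/45% the mean log-odds ratio is about −1.0, so τ = 1.0 would mean about 16% of buyers purchase more easily in uniform. That is an upper case. These measures do not make τ zero, and re-randomizing buyer numbers in each city spreads buyers over clusters without adding buyers to the contrast.
- **Exploratory status.** The plan says these analyses explore, and its 0.05 rule (Protocol 8.1, SAP 2.3.1) covers differences between the attire groups. It would be too much to say that the plan commits to declaring interactions at p < 0.05. This limits the seriousness of the point. The inflation at τ = 0 also comes from the wider absence of cluster adjustment and is not special to sex or age.

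**Conclusion.** The point holds conditionally. If buyer gender and age are meant, the sample for these contrasts is 25 buyers, and the store-level methods named in the plan are anti-conservative: about 7-18% false positives with a common attire effect, and about 25% at slope SD 1.0. Buyer-day clustering would be an adequate repair only if attire effects differ little between buyers. Its error rate is 5-6% at slope SD 0, 7-11% at 0.5 and 10-19% at 1.0, with the lower ends at ICC 0.5. A test with the buyer as the unit holds about 5%.

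The slope SD, the purchase rates and the age split are assumptions. The near-5% result for the buyer-level test also assumes that male and female buyers have the same baseline rate. With a constant odds ratio but female baseline log-odds higher by 1.0 or 1.5, a t-test on rate differences rejects 12% or 29% of the time, because a constant odds ratio is then not a constant risk difference. The choice of scale is therefore part of the hypothesis. The analysis is exploratory, so this is a worthwhile correction and no threat to the primary comparison.

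**What to change.** In Protocol 8.5 and SAP 2.3.5:

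1. State whose gender and age are meant.
2. For buyer gender and buyer age, test the attire interaction with the buyer as the unit, on one scale chosen in advance. The options are a logistic model with a buyer-specific attire slope (odds-ratio scale), or a comparison of each buyer's uniform-minus-casual purchase rate by t or permutation test (risk-difference scale; 25 − 2 = 23 degrees of freedom). They test different hypotheses and are not interchangeable. The mixed model was not simulated here. With an uneven age split, standard errors clustered on buyer are not a safe substitute (step 4).
3. Label the result exploratory, and report no store-level interaction p-value for these two factors.
4. For seller gender and age, which vary by store, the cluster adjustment is enough.

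The cost is SAP wording and a few lines of code. Buyer identity is already collected (Protocol Appendix 4, item 2). The price is wider intervals for the two buyer contrasts.

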8.6. Sample size considerations

Successful purchase rates of e-cigarette products for the school uniform group and the casual attire group will be derived from the pilot study. Other parameters required for the cluster-RCT sample size calculation are as follows:

- Randomization in a 1:1 ratio
- $\alpha = 0.05$ (two-sided)
- power = 0.85
- cluster size = 4 (both for intervention group and control group)
- inter-cluster correlation coefficient = 0.5 (default)

However, considering the primary goal of this study is to characterize e-cigarette seller behaviors at a national level, we decide to set the final sample size to be approximately 1,080, which may be far more than the minimum sample required (about 3 times) for testing the effect of buyer attire on e-cigarette sales to adolescents.

8.7. Missing data

Since simulated buyers use the instrument embedded in an online survey platform to fill out the collected information, there is no chance that they will miss any questions as the system will remind them of any potential missing values. The pilot survey will help us confirm which questions can be filled in, considering the possibility that the adolescents may be asked to leave by the sellers for not being able to show proof of age as soon as he/she enters the store. While filling in questions regarding the store external environment, simulated buyers can select "Unable to observe" and skip questions that cannot be answered. Missing data on the store internal environment due to the reason of being asked to leave will not affect our main analysis. For the in-store environmental characteristics, only subjects with available data will be included in the analyses.

9. Quality control

9.1. Design phase of the protocol

- Provide trainings to simulated buyers with a study manual and effective communication skills to ensure the quality of research in the fieldwork;
- Prior to study implementation, a pilot survey will be carried out using the designed assessing tool. Subsequently, we will modify the tool based on seller responses and preliminary results to improve its operability and accuracy of information collected.
- Data input will be completed an online self-developed assessing tool, eliminating the possibility of missing critical items.

